## **2.5 Concomitant Medications**

### **2.5.1 Prior and Concomitant Medications**

Prior medications are defined as medications that were taken within 30 days prior to initial dosing with study drug.

Concomitant medications are defined as medications taken any time after the start of dosing until discharge assessments. All concomitant medication, including blood and blood products, dietary supplements, and non-prescription drugs, will be listed at screening/baseline. Each entry will include the treatment's start date, treatment name (Generic), reason for use, dosing regimen (dose and frequency of use), route of administration, and stop date (if applicable). The clinical significance of the medication use will be decided by the investigator. Study subjects will be routinely questioned for changes in the administration of concomitant medication during the trial and changes should be updated from medical records as well.

## **3.0 STUDY POPULATION**

The study population will be male or female adult healthy volunteers age 18 to 65 years who have consented to participate in this study.

### **3.1 Inclusion Criteria**

1. For a subject to be eligible for this study, he or she must meet **all** of the following criteria: Is a male or female subject between the ages of 18 and 65 years, inclusive.
2. Has body mass index (BMI) between >22 and <40.
3. Has SMF bulge that is contiguous and fits to 32±4 injections sites according to a grid with 1 centimeter (cm) distance between injection points.
4. Has grade 3 to 4 of SMF as rated by the C-CAT.
5. Has a visible or large pocket of submental fat- according to physician global assessment.
6. Has grade 3 to 4 of SMF as rated by the S-CAT.
7. Has stable weight, with no fluctuation of >5 kg in the past 12 months.
8. If female, is not pregnant or breastfeeding based on the following:
  - a. agree to the use of highly effective contraceptive methods for at least 2 weeks before baseline until 4 weeks after the last day of study drug and a negative serum pregnancy test ( $\beta$ -hCG) at screening and negative urine pregnancy test at baseline; or
  - b. is of nonchildbearing potential defined as clinically infertile as the result of surgical sterilization (hysterectomy, bilateral tubal ligation, and/or bilateral oophorectomy); or
  - c. is confirmed postmenopausal status (defined as either having amenorrhea for  $\geq$  12 consecutive months without another cause and documented serum follicle-stimulating hormone (FSH) level  $>$  40 mIU/mL or another documented medical condition (e.g., was born without a uterus))

NOTE: The following are considered highly effective contraceptive methods: hormonal oral contraceptives, injectables, and patches; intrauterine devices; double-barrier methods (synthetic condom, diaphragm, or cervical cap used with spermicidal foam, cream, or gel); and male partner sterilization.

9. If male (with or without vasectomy), agree to the use of highly effective contraceptive methods e.g., condom , from study check-in until 7 days after the last day of study drug.
10. Is willing to avoid strenuous exercise for seven (7) days post treatment.
11. Is able to adhere to the visit schedule and protocol requirements and be available to complete the study.
12. Is willing and able to sign an Institutional Review Board (IRB) approved informed consent form (ICF) indicating that they are aware of the investigational nature of the study.

### 3.2 Exclusion Criteria

Subjects must **NOT** meet any of the following Exclusion criteria to be eligible for enrollment:

1. Is unable to tolerate subcutaneous injections.
2. Has dysfunctional gallbladder activity (e.g., underwent cholecystectomy or cholecystitis).

3. Has any uncontrolled systemic disease that is not stabilized (i.e., cardiovascular disease, mental illness).
4. Has had treatment with botulinum toxin injections in the neck or chin area within nine (9) months prior to screening.
5. Has used anticoagulation therapies that may increase bleeding or bruising (i.e., aspirin, ibuprofen, vitamins, and herbal preparations) for seven (7) days prior to treatment.
6. Has skin laxity (i.e., elastosis, skin crepiness, skin redundancy, skin draping, vertical and/or horizontal skin bands and folds, blunting of cervical mental angle, loss of opposition of skin to underlying neck structures due to skin laxity) that could obscure the evaluation and treatment of SMF.
7. Has any scars, unshaven hair, tattoos, facial hair or jewelry on or near the proposed treatment area.
8. Has presence of structures or confounding factors that may interfere with assessing SMF such as but not limited to enlarged submandibular salivary and/or parotid glands, micrognathia, chin implant, soft tissue volume augmentation of chin and/or jawline, pronounced platysmal bands and deep necklace lines or presence of facial jowls that could obscure the evaluation of SMF.
9. Has a fat bulge under the chin that is too large to be adequately treated by 32+/-4 contiguous injections on a 1cm grid .
10. Has a fat bulge under the chin that is of an insufficient volume to allow 28 injections within a contiguous 1 cm grid.
11. Has significant history or current evidence of a medical, psychological or other disorder that, in the Investigator's opinion, would preclude enrollment in the study.
12. Has an active dermatitis or open wound in the proposed treatment area.
13. Has abnormal coagulation tests (PT, PTT)
14. Has D-dimer value >0.64mg/L in screening visit
15. Has an active bacterial, fungal, or viral infection in the proposed treatment area.
16. Has a pre-existing skin condition in the submental region that, at the Investigator's discretion, may confound evaluation or analysis.

17. Has previously had treatments or surgery in the submentum, such as but not limited to, focused ultrasound, radiofrequency, cryolipolysis, liposuction, sodium deoxycholate, or neck lift.
18. Has pre-existing neurological or gastrointestinal condition leading to dysphagia, dysphonia, or facial nerve palsy.
19. Has Dercum's Disease
20. Has allergic reactions to injectables.
21. Has any pre-existing medical condition other than increased SMF that, at the Investigator's discretion, may result in increased submental fullness, such as but not limited to, thyroid enlargement, goiter, cervical lymphadenopathy, etc.
22. Has a planned fat reduction procedure of any variety to the submental region for the duration of the study.
23. Has medication or a history of coagulopathy.
24. Has a history or family history of venous thrombotic disease.
25. Has been treated chronically at least three (3) months prior to study entry with systemic steroids or immunosuppressive drugs.
26. Has been treated chronically at least one (1) week prior to study entry with non-steroidal anti-inflammatory drugs (NSAIDs).
27. Current participation or participation within three (3) months prior to the start of this study in a drug or other investigational research study.
28. Has claustrophobia or an MRI incompatible device or implant.

### **3.3     Subject Identification**

At each site, a unique code numbers will be assigned by the Investigator to the trial subject rather than the subjects' name, personal identification numbers, and/or addresses to protect the subject's identity. The code numbers and initials will be used in lieu of the subject's name when the Investigator reports AE and/or other trial related data.

### **3.4 Removal, Replacement or Early Withdrawal of Subjects from the Assessment Not Due to Intolerable Side Effects**

Subjects experiencing serious side effects will be withdrawn from the study, but will be followed until the event resolves or becomes stable. If a subject is withdrawn or removed from the study due to serious side effects, the subject will not be replaced.

## **4.0 STUDY PROCEDURES AND ASSESSMENTS**

### **4.1 Informed Consent**

Prior to initiation of any study procedures, each subject will undergo an Informed Consent process in which the subject voluntarily confirms their willingness to participate in the trial. The Investigator or his/her approved designee must explain the nature of the study protocol and associated risks to the potential study participant. The potential participant must be allowed to review the study information and to ask questions before being asked to sign the Informed Consent Form (ICF). Written informed consent must be provided by the potential study participant prior to initiation of any screening evaluations or other study-related procedures. The signature date and the name of the individual at the site who obtained the informed consent will be recorded in the subject's medical record.

The ICF approved by the IRB/EC will contain a description of the study's purpose, purpose, procedures, inconveniences and potential risks, and anticipated benefits. Prior to participation in the trial, the subject will receive a copy of the signed and dated written ICF. During participation in the trial, the subject will receive a copy of the signed and dated consent form updates and a copy of any amendments to the ICF provided to the subjects.

After written informed consent is obtained, the subject will be assigned a screening number and will undergo the designated screening procedures listed in Appendix A. The Investigator, sub-investigator or delegate will assess the results of these screening evaluations to determine eligibility for entry into the study according to the inclusion/exclusion criteria listed in [Section 3.0](#).

### **4.2 Complete physical examination**

The Investigator (or medically qualified nominee) will perform a complete physical exam at screening and on Day 84. Additional examinations that will be performed during the screening include height and weight to determine BMI to confirm eligibility.

A skin type score using Fitzpatrick Skin Type will be performed. Skin type will be assessed prior to injection in order to determine skin sensitivity to treatment. The Fitzpatrick scale is based on six (6) categories of skin as described below:

Type I	Light, pale white	Always burns, never tans
Type II	White, fair	Usually burns, tans with difficulty
Type III	Medium, white to olive	Sometimes mild burn, gradually tans to olive
Type IV	Olive, moderate brown	Rarely burns, tans with ease to moderate brown
Type V	Brown, dark brown	Very rarely burns, tans very easy
Type VI	Black, very dark brown to black	Never burns, tans very easily, deeply pigmented

#### **4.3 Medical History**

A medical history will be obtained at screening. Subject's medical history should be fully documented to confirm eligibility. Medical history must include, but not limited to, past and present medical conditions, concomitant non-drug treatments, and hypersensitivity to drugs.

#### **4.4 Vital Signs**

Vital signs (systolic and diastolic sitting position blood pressure, pulse rate, respiratory rate, and body oral temperature) are to be obtained at screening to ensure compliance.

Additional vital sign measurements to assess subject's safety will be performed at baseline (Day 0) prior to treatment and after treatment, Day 1, and during study visits on Days 7, 28, and 56.

#### **4.5 ECG**

ECG test is to be obtained at screening to ensure compliance. ECG will be done in triplicates.

Additional ECG will be performed on Day 7 and Day 84 visit.

#### **4.6 Height and Weight**

Height will be reported in centimeters at screening. Body weight will be reported in kilograms (kg) at screening.

Weight measurement will be performed at screening to determine the BMI value. An additional weight measurement will be performed at baseline and at study visits on Days 56 and 84 to verify no significant changes in weight throughout the assessment of SMF changes during the study.

#### **4.7 Clinical Laboratory Evaluations – Hematology and Serum Chemistry**

Screening blood samples and urine specimens for laboratory evaluation will be collected at screening to confirm eligibility. Additional blood samples will be collected at Day 1, 7, 28 and Day 84 study visits for an assessment of hematology and serum chemistry.

If there are clinically significant alerts obtained at any visit, an unscheduled visit will be added for additional blood sampling.

##### **4.7.1 Hematology**

Complete blood cell count (CBC) will include a standard red blood cell (RBC), white blood cell (WBC) with differential, hemoglobin, hematocrit, platelets, D-dimer, Fibrinogen and coagulation (International normalized ratio [INR], partial thromboplastin time [PTT] and prothrombin time [PT]).

##### **4.7.2 Serum Chemistry**

Comprehensive metabolic panel will include serum alkaline phosphatase (ALP), alanine aminotransferase (ALT), aspartate aminotransferase (AST), glucose, calcium, globulin (calculated), phosphorus, chloride, sodium, potassium, blood urea nitrogen (BUN)/creatinine ratio (calculated), creatinine with GFR estimated, total bilirubin, albumin, albumin/globulin ratio (calculated), total protein, amylase, bicarbonate/carbon dioxide (CO2), uric acid, gamma-glutamyl transferase (GGT), and lactate dehydrogenase (LDH).

##### **4.7.3 Pregnancy Tests**

A serum ( $\beta$ -hCG) pregnancy test will be administered to females of childbearing potential at screening and a urine pregnancy test will be administered at baseline prior to dosing. Additional serum pregnancy tests will be done at any time during the study (up to 84 days), if pregnancy is suspected.

#### **4.8 Submental Fat Thickness using Calipers**

The aim of caliper measurement is to evaluate fat reduction before and after treatment. At screening, caliper measurement will be made with the subject's head maintained in a neutral position. The caliper will be positioned to pinch the skin at 15 mm on either side of the center point of the submental area.

Additional measurement to assess efficacy will be conducted at study visits at Days 28, 56, and 84.

#### **4.9 2-D Standardized Photography**

Standardized photography (2-dimensional) of the face (SMF area) will be conducted at screening in order to establish a baseline value for assessment of treatment efficacy.

Additional photography will be conducted on Days 1, 7, 28, 56, and 84 to evaluate qualitative changes in SMF area at study visits.

Photographs will be taken with a digital camera according to photography standards in dermatology surgeries for the face/neck area (see [Appendix B](#)).

#### **4.10 Magnetic Resonance Imaging (MRI)**

The purpose of the MRI exam is to evaluate fat reduction following treatment. MRI exams will be conducted in imaging centers close to selected clinical sites.

MRI will be conducted at screening in order to establish a baseline value for assessment of treatment efficacy. Post-treatment period MRI will be completed within 84 days ( $\pm$  14 days) after the treatment session.

Quantitative measurements such as fat volume of the SMF area will be used as an objective parameter for measurement of SMF reduction following treatment.

Sagittal 2D and 3D images of the head and neck (chin area) will be obtained using 1.5 Tesla machine (General Electric, Siemens, Phillips or other). For each MRI visit, the total imaging time is expected to be approximately thirty (30) minutes.

During the imaging, subjects will be positioned in Head first Supine recumbent. Images in the sagittal plane across the entire submental region will be collected using an appropriate MR sequence to minimize the effects of air cavities, dental implants, and amalgam on the resultant MR image. This imaging approach will generate a 2D and 3D image data set that allows for the quantification of the SMF volume in several slices covering the treatment area. In the follow up MRI exam, slices will be positioned as similar as possible to the first MRI exam.

Images should be saved in a DICOM format and include the date completed and subject's screening number to be transferred home the Sponsor's request for central analysis.

Submental volume analysis will be performed by computer-assisted tools and calculation of submental volume will be completed prior to dosing and after treatment.

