### **2.1.2 Secondary Objectives**

The secondary objectives of this study are as follows:

- to determine the efficacy of RZL-012 versus placebo on SMF reduction measured on Day 84 versus baseline using both Subject Self-Chin Assessment Tool (S-CAT) and the Clinician Assessment Tool (C-CAT);
- to assess the reduction in SMF on Day 84 versus baseline using the caliper measured submental thickness and magnetic resonance imaging (MRI);
- to assess the safety of RZL-012 in the treatment of SMF reduction.

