## 8.1 Screening (Days -28 to -1)

The Investigator or his/her approved designee must explain the nature of the study protocol and associated risks to the potential study participant. The potential participant must be allowed to review the study information and to ask questions before being asked to sign the Informed Consent Form (ICF). Written informed consent must be provided by the potential study participant prior to initiation of any screening evaluations or other study-related procedures. The signature date and the name of the individual at the site who obtained the informed consent will be recorded in the subject's medical record.

After written informed consent is obtained, the subject will be assigned a screening number and will undergo the designated screening procedures listed in Appendix A. The Investigator, sub-investigator or delegate will assess the results of these screening evaluations to determine eligibility for entry into the study according to the inclusion/exclusion criteria listed in [Section 3.0](#).

Screening evaluations may be performed up to 28 days in advance of dosing but must be completed at least 1 day prior to Day 0.

The following study evaluations and procedures are required to determine eligibility at pre-screening visit:

- C-CAT
- S-CAT
- 2D photography

The following study evaluations and procedures are required to determine eligibility in the second part of the screening visit:

- Obtain and record a medical history, including demographics, prior medications, and concomitant medications.
- Complete physical examination
- Vital signs
- ECG
- Height and weight measurements
- Blood and serum samples for the following laboratory evaluations:
  - Hematology
  - Serum chemistry
  - Coagulation

- Pregnancy (if applicable)
- Caliper measurement of SMF thickness
- MRI
- Physicians Global Assessment Question
- Subject's satisfaction questionnaire (appearance of submental area)
- Subject Global Assessment questions
- Subject's impact questionnaire

Subjects may be re-screened if they were screened and not dosed within 28 days. The following procedures will be performed: vital signs and weight measurements.

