The Chi-Square test will be applied to test the statistical difference between the placebo group and the RZL-012 high-dose group in responder rate at Day 84. Responder rate is defined as the percentage of subject achieving at least a 1-grade improvement from baseline in C-CAT.

- **Analysis of secondary Endpoints**

Secondary endpoints (improvement in 1 point in S-CAT and C-CAT, improvement in 2 points in both S-CAT and C-CAT) will be tested using a two-sided test of equality of binomial proportions at the alpha=0.05 level of significance.

All other secondary endpoints will be tested using a two-sided test at the alpha=0.05 level of significance.

- The Chi-Square test will be applied to test the statistical difference between the placebo group and each of the RZL-012 dose groups in the responder rate at Day 84 where responder rate is defined as the percentage of subject achieving at least a 1-grade improvement from baseline in both S-CAT and C-CAT.
- The change and percentage of change from baseline at Day 84 in SMF thickness measured with caliper and in SMF volume by MRI will be calculated along with 95% Confidence intervals.

The Paired T-test for two means (paired observations) will be applied for testing the statistical significance of the change and percentage of change from baseline at Day 84 in SMF thickness measured with caliper and in SMF volume by MRI within each study group.

MediStat Statistics in Medicine	DOCUMENT NUMBER: 140-BST-PLN-001	PAGE: 15 of 16
TITLE: Statistical Analysis Plan of Protocol Number RZL-012-SMF-P2bUS-001	EFFECTIVE DATE : 08/03/2022 REVISION NUMBER : 1.0	

The two-sample T-test for independent samples will be applied for testing the statistical significance of the change and percentage of change from baseline at Day 84 in SMF thickness measured with caliper and in SMF volume by MRI between each of the RZL-012 dose groups and the placebo group.

- Analysis of Exploratory endpoint
  - SMF improvement

The SMF improvement using the Global Aesthetic Improvement Scale (GAIS) , the physician Global Assessment of Change Scale, Subjects Global Self-Assessment of Change Scale, Subject Global Assessment of Change Scale, the subject's satisfaction questionnaires, and the subjects's impact questionnaire will be summarized at each timepoint and by treatment group.

- Analysis of Safety

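### The plan does not mask the MRI reader to scan date or order, which can bias the within-arm volume reductions and paired t-tests; the dose-versus-placebo comparison is largely protected

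*Protocol*

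**What the plan says.** Protocol section 4.10 says that SMF volume "will be used as an objective parameter for measurement of SMF reduction following treatment". On file handling it states: "Images should be saved in a DICOM format and include the date completed and subject's screening number". The files then go to a central analysis. On timing it states that "calculation of submental volume will be completed prior to dosing and after treatment", using computer-assisted tools whose degree of automation is not described. It also states: "In the follow up MRI exam, slices will be positioned as similar as possible to the first MRI exam".

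Protocol section 8.1 says "Screening evaluations may be performed up to 28 days in advance of dosing", and section 4.10 says "Post-treatment period MRI will be completed within 84 days", with a window of ±14 days. Footnote f of the SAP schedule gives ±7 days for the same scan.

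Protocol section 8.3 blinds the Investigator, the clinical staff and the subjects, and only to treatment group. Neither document says who reads the scans. Neither mentions masking to visit or order, paired reading, a second reader or a repeatability check.

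One secondary objective (Protocol 2.1.2) is "to assess the reduction in SMF on Day 84 versus baseline using the caliper measured submental thickness and magnetic resonance imaging (MRI"). The endpoint that implements it (Protocol 2.3.2, repeated in the SAP) compares the RZL-012 groups with placebo. SAP section 6 plans both kinds of test: two-sample t-tests of each dose against placebo, and, within each study group, "The Paired T-test for two means (paired observations) will be applied for testing the statistical significance of the change".

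**The concern.** A date on the file tells the reader which scan came first, unless a step outside these documents removes it. If the baseline volume is finished before dosing, that reading cannot be blind to order at all, and the two volumes of a subject come from sessions separated by the whole follow-up. A reader who expects fat to shrink may then measure the later scan slightly smaller, in every arm. Drift in reading practice between sessions would add further error.

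The first effect bears on the estimated reduction within each arm and on the paired t-tests. The second bears on the precision of every MRI comparison. No criterion in Protocol sections 3.1 or 3.2 uses an MRI volume. Section 8.1 does list MRI among the screening procedures, but sets no volume limit, and Appendix A places the scan after the subject has met all screening criteria. Nothing in the plan therefore needs a baseline volume before dosing.

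**Working it through.** **The plan's own figure.** No sample size or power is stated for MRI. The stated calculation is for C-CAT: 70% versus 35%, two-sided alpha 0.05, power 90%. With pooled variance under the null and mean proportion 0.525, n = [1.960·√(2·0.525·0.475) + 1.282·√(0.70·0.30 + 0.35·0.65)]² / 0.35² = 40.7, so 41 per group, as stated. The planned 45 allows a loss of 4/45 = 8.9%. I use n = 41 and n = 45 below.

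**Time between scans.** With the Protocol window, the shortest gap is 1 + (84 − 14) = 71 days and the longest is 28 + (84 + 14) = 126 days, about 10 to 18 weeks. With the SAP window it is 78 to 119 days.

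**Inputs for MRI.** Protocol section 1.2.4.1.4 gives the phase 2a volume changes: high dose −22.2% ± 14.9, low dose −10.6% ± 14.5, placebo −0.4% ± 13.9. I take ± to be an SD. The differences from placebo are 21.8 points (high) and 10.2 points (low). The sizes of shift and drift are assumptions.

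**Shift within an arm.** Suppose placebo has no true change and every Day 84 reading is shifted by b points. The paired t-test then follows a non-central t with n − 1 degrees of freedom and non-centrality b/(13.9/√n). The standard error is 13.9/√41 = 2.17 or 13.9/√45 = 2.07.

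| Assumed shift b (points) | Non-centrality, n=41 / 45 | Chance of p<0.05, n=41 | n=45 |
|---|---|---|---|
| 0 | 0 / 0 | 5.0% | 5.0% |
| 1 | 0.46 / 0.48 | 7.3% | 7.6% |
| 2 | 0.92 / 0.97 | 14.7% | 15.7% |
| 3 | 1.38 / 1.45 | 27.1% | 29.4% |
| 5 | 2.30 / 2.41 | 61.3% | 65.5% |

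**Shift between arms.** If every arm is shifted by the same b, the difference is (active + b) − (placebo + b) = active − placebo. The bias is zero.

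**Session drift.** Independent read error with SD e in the change score raises each arm's SD to √(SD² + e²). The two-sample t-test has 2n − 2 degrees of freedom and non-centrality equal to the difference divided by √[(s₁² + s₂²)/n]. For low dose versus placebo, n = 41:

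| Assumed added SD e | SD low / placebo | Standard error | Power |
|---|---|---|---|
| 0 | 14.5 / 13.9 | 3.14 | 89.5% |
| 3 | 14.8 / 14.2 | 3.21 | 88.2% |
| 5 | 15.3 / 14.8 | 3.33 | 85.8% |
| 7 | 16.1 / 15.6 | 3.50 | 82.2% |

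High dose versus placebo stays above 99% throughout.

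**The case against.** The strongest reply is that the MRI endpoint is placebo-controlled. A common shift cancels there, a spurious reduction in the placebo arm does not favour the drug, and the primary endpoint is C-CAT. This stands, and it limits the point to the within-arm estimates and paired tests plus some loss of precision.

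A second reply is that every error size is assumed. This also stands: at 1 point the inflation is slight, and the phase 2a placebo mean of −0.4% shows no sign of a shift of several points. That is weak reassurance, because it rests on 10 placebo subjects and an undescribed reading method.

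A third reply is that a date and coded number on an image file are ordinary traceability, and that the timing sentence may only mean that volumes are calculated for both scans. An imaging manual that was not supplied might mask the reader. These replies are fair, but the literal wording favours sequential reading, dated files can reveal order on either reading, and the plan itself requires no masking.

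A reader might infer several stronger things that the documents do not support:

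- **The reader certainly knows the order.** The text governs how files are saved and transferred, not what the reader sees.
- **Fat is outlined by subjective judgement.** The tools are called computer-assisted; how far they are automated is not stated.
- **The dose-versus-placebo result is biased.** That would need a reader who also knows or guesses the arm, and nothing says that the reader has treatment codes.
- **A subject may change scanner between visits.** Section 4.10 lists acceptable makes and is silent on this. It is a question of image acquisition, separate from masking.

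**Conclusion.** The point holds as a gap in the plan: scan order is not hidden from the MRI reader, and a literal reading of section 4.10 produces unmasked sequential readings. The consequence falls on the within-arm MRI reductions and their paired t-tests. How large it is cannot be known from the documents; the illustration runs from almost harmless at a 1-point shift (7-8% false positives) to serious at 5 points (61-66%). It assumes an equal shift for every subject and a phase 2a SD of 13.9.

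For the dose-versus-placebo MRI endpoint the effect is a modest loss of precision, at most about 7 percentage points of power for low dose over the drift range examined, and negligible for high dose. The primary C-CAT analysis is not touched. The change is worth making because it is cheap and because the plan presents MRI as its objective measure.

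**What to change.** In Protocol section 4.10:

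- Recode the scans before reading, so that the reader sees neither date nor visit. Date and screening number can stay in a separate key for traceability.
- After the Day 84 scan, have one reader, masked to treatment and visit, measure each subject's two scans in one session and in random order.
- Remove the pre-dose timing for the endpoint volume. If a pre-dose volume is wanted for another purpose, read that scan again within the masked pair and use the second reading for the endpoint.

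The ±14-day and ±7-day windows for the follow-up MRI should be reconciled in the same amendment.

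The cost is a change of wording and a recoding step. No extra scan, reader or subject is needed. The downside is that endpoint baseline volumes become available only after follow-up; no eligibility criterion or planned analysis uses them sooner.
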